## 14.3 Safety Data

### 14.3.1 Displays of Adverse Events

**Table 23: Overall Summary of Adverse Events**

	3 mg/kg EV68-228-N (N=X)		10 mg/kg EV68-228-N (N=X)		30 mg/kg EV68-228-N (N=X)		Placebo (N=X)		All Participants who Received Active Product (N = x)	
Participants a with	n	%	n	%	n	%	n	%	n	%
At least one solicited adverse event	x	xx	x	xx	x	xx	x	xx	x	xx
At least one unsolicited adverse event	x	xx	x	xx	x	xx	x	xx	x	xx
At least one related unsolicited adverse event	x	xx	x	xx	x	xx	x	xx	x	xx
Mild (Grade 1)	x	xx	x	xx	x	xx	x	xx	x	xx
Moderate (Grade 2)	x	xx	x	xx	x	xx	x	xx	x	xx
Severe (Grade 3)	x	xxx	x	xx	x	xx	x	xx	x	xx
Life-threatening (Grade 4)	x	xx	x	xx	x	xx	x	xx	x	xx
Death (Grade 5)										
At least one severe (Grade 3 or higher) unsolicited adverse event										
Related										
Unrelated										
At least one serious adverse event b										
At least one related, serious adverse event										
At least one adverse event leading to early termination c										
At least one unanticipated problem (UPs)										
At least one medically attended adverse event (MAAEs)										
At least one new onset chronic medical conditions (NOCMCs)										

Note: N=Number of participants in the Safety Population.

a Participants are counted once for each category regardless of the number of events.

b A listing of Serious Adverse Events is included in Section 14.3.2.

c As reported on the Adverse Event eCRF.

**Table 24: Adverse Events Occurring in  $\geq 5\%$  of Participants in Any Dose Cohort by MedDRA System Organ Class and Preferred Term and Dose Cohort**

[Implementation Note: This table will report both solicited and unsolicited AEs.]

MedDRA System Organ Class	MedDRA Preferred Term	3 mg/kg EV68-228-N (N=X)			10 mg/kg EV68-228-N (N=X)			30 mg/kg EV68-228-N (N=X)			Placebo (N=X)			All Participants who Received Active Product (N=X)		
		n	%	Events	n	%	Events	n	%	Events	n	%	Events	n	%	Events
Serious Adverse Events																
All	All	x	xx	x	x	xx	x	x	xx	x	x	xx	x	x	xx	x
SOC1	All															
	PT1															
	Etc.															
	All															
	PT1	x	xx	x	x	xx	x	x	xx	x	x	xx	x	x	xx	x
Etc.	Etc.															
Other (Non-serious) Adverse Events																
All	All	x	xx	x	x	xx	x	x	xx	x	x	xx	x	x	xx	x
SOC1	All	x	xx	x	x	xx	x	x	xx	x	x	xx	x	x	xx	x
	PT1															
	Etc.															
Etc	Etc															

Notes: N=Number of participants in the Safety Population. n=Number of participants reporting an event. Events=Total frequency of events reported.

### 14.3.1.1      **Solicited Adverse Events**

**Table 25:      Number and Percentage of Participants Experiencing Solicited Events with 95% Confidence Intervals by Symptom and Dose Cohort**

Symptom	3 mg/kg EV68-228-N (N=X)			10 mg/kg EV68-228-N (N=X)			30 mg/kg EV68-228-N (N=X)			Placebo (N=X)			All Participants who Received Active Product (N=X)		
	n	%	95% CI	n	%	95% CI	n	%	95% CI	n	%	95% CI	n	%	95% CI
Any Symptom	x	xx	x.x, x.x	x	xx	x.x, x.x	x	xx	x.x, x.x	x	xx	x.x, x.x	x	xx	x.x, x.x
Headache															
Rash															
Nausea															
Vomiting															
Diarrhea															
Fatigue (Tiredness)															
Myalgia (Body aches/Muscular pain)															

Notes: N=Number of participants in the Safety Population. 95% CI=Clopper-Pearson confident interval.

**Table 26: Comparison of the Proportion of Participants Experiencing Solicited Events by Dose Cohort**

Symptom	Statistic	3 mg/kg EV68-228-N (N=X)	10 mg/kg EV68-228-N (N=X)	30 mg/kg EV68-228-N (N=X)	Placebo (N=X)
Any Symptom	Proportion	X.XX	X.XX	X.XX	X.XX
	95% CI (for proportion) a	X.XX, X.XX	X.XX, X.XX	X.XX, X.XX	X.XX, X.XX
	Difference	X.XX	X.XX	X.XX	-
	95% CI (for difference) b	X.XX, X.XX	X.XX, X.XX	X.XX, X.XX	-
Headache	Proportion	X.XX	X.XX	X.XX	X.XX
	95% CI (for proportion)	X.XX, X.XX	X.XX, X.XX	X.XX, X.XX	X.XX, X.XX
	Difference	X.XX	X.XX	X.XX	-
	95% CI (for difference)	X.XX, X.XX	X.XX, X.XX	X.XX, X.XX	-
Rash	Proportion	X.XX	X.XX	X.XX	X.XX
	95% CI (for proportion)	X.XX, X.XX	X.XX, X.XX	X.XX, X.XX	X.XX, X.XX
	Difference	X.XX	X.XX	X.XX	-
	95% CI (for difference)	X.XX, X.XX	X.XX, X.XX	X.XX, X.XX	-
Nausea	Proportion	X.XX	X.XX	X.XX	X.XX
	95% CI (for proportion)	X.XX, X.XX	X.XX, X.XX	X.XX, X.XX	X.XX, X.XX
	Difference	X.XX	X.XX	X.XX	-
	95% CI (for difference)	X.XX, X.XX	X.XX, X.XX	X.XX, X.XX	-
Vomiting	Proportion	X.XX	X.XX	X.XX	X.XX
	95% CI (for proportion)	X.XX, X.XX	X.XX, X.XX	X.XX, X.XX	X.XX, X.XX
	Difference	X.XX	X.XX	X.XX	-
	95% CI (for difference)	X.XX, X.XX	X.XX, X.XX	X.XX, X.XX	-
Diarrhea	Proportion	X.XX	X.XX	X.XX	X.XX
	95% CI (for proportion)	X.XX, X.XX	X.XX, X.XX	X.XX, X.XX	X.XX, X.XX
	Difference	X.XX	X.XX	X.XX	-
	95% CI (for difference)	X.XX, X.XX	X.XX, X.XX	X.XX, X.XX	-
Fatigue (Tiredness)	Proportion	X.XX	X.XX	X.XX	X.XX
	95% CI (for proportion)	X.XX, X.XX	X.XX, X.XX	X.XX, X.XX	X.XX, X.XX
	Difference	X.XX	X.XX	X.XX	-
	95% CI (for difference)	X.XX, X.XX	X.XX, X.XX	X.XX, X.XX	-
Myalgia (Body aches/Muscular pain)	Proportion	X.XX	X.XX	X.XX	X.XX
	95% CI (for proportion)	X.XX, X.XX	X.XX, X.XX	X.XX, X.XX	X.XX, X.XX
	Difference	X.XX	X.XX	X.XX	-
	95% CI (for difference)	X.XX, X.XX	X.XX, X.XX	X.XX, X.XX	-

Note: N=Number of participants in the Safety Population.

a95% CI=Clopper-Pearson confidence interval.b95% CI=Wald confidence interval.

**Table 27: Number and Percentage of Participants Experiencing Solicited Events by Symptom, Maximum Severity, and Dose Cohort**

Symptom	Severity	3 mg/kg EV68-228-N (N=X)		10 mg/kg EV68-228-N (N=X)		30 mg/kg EV68-228-N (N=X)		Placebo (N=X)		All Participants who Received Active Product (N=X)	
		n	%	n	%	n	%	n	%	n	%
Any Symptom	None	x	xx	x	xx	x	xx	x	xx	x	xx
	Mild										
	Moderate										
	Severe										
	Life-threatening										
Headache	None	x	xx	x	xx	x	xx	x	xx	x	xx
	Mild										
	Moderate										
	Severe										
	Life-threatening										
Rash	None	x	xx	x	xx	x	xx	x	xx	x	xx
	Mild										
	Moderate										
	Severe										
	Life-threatening										
Nausea	None	x	xx	x	xx	x	xx	x	xx	x	xx
	Mild										
	Moderate										
	Severe										
	Life-threatening										
Vomiting	None	x	xx	x	xx	x	xx	x	xx	x	xx
	Mild										
	Moderate										
	Severe										
	Life-threatening										
Diarrhea	None	x	xx	x	xx	x	xx	x	xx	x	xx
	Mild										
	Moderate										
	Severe										
	Life-threatening										
Fatigue (Tiredness)	None	x	xx	x	xx	x	xx	x	xx	x	xx
	Mild										

**Table 27: Number and Percentage of Participants Experiencing Solicited Events by Symptom, Maximum Severity, Dose, and Dose Cohort (continued)**

Symptom	Severity	3 mg/kg EV68-228-N (N=X)		10 mg/kg EV68-228-N (N=X)		30 mg/kg EV68-228-N (N=X)		Placebo (N=X)		All Participants who Received Active Product (N=X)	
		n	%	n	%	n	%	n	%	n	%
	Moderate										
Myalgia (Body aches/Muscular pain)	Severe										
	Life-threatening										
	None	X	XX	X	XX	X	XX	X	XX	X	XX
	Mild										
	Moderate										
Fatigue	Severe										
	Life-threatening										

Notes: N=Number of participants in the Safety Population. Severity is the maximum severity reported over all solicited symptoms post dosing for each participant.

**Table 28: Number and Percentage of Participants Experiencing Solicited Events by Symptom, Severity, and Day Post Dosing – 3 mg/kg EV68-228-N**

Symptom	Severity	3 mg/kg EV68-228-N (N=X)							
		Day 1		Day 2		Day 3		Ongoing After Day 3	
		n	%	n	%	n	%	n	%
Any Symptom	None	X	XX	X	XX	X	XX	X	XX
	Mild								
	Moderate								
	Severe								
	Life-threatening								
	Not Reported								
Headache	None								
	Mild								
	Moderate								
	Severe								
	Life-threatening								
	Not Reported								
Rash	None								
	Mild								
	Moderate								
	Severe								
	Life-threatening								
	Not Reported								
Nausea	None								
	Mild								
	Moderate								
	Severe								
	Life-threatening								
	Not Reported								
Vomiting	None								
	Mild								
	Moderate								
	Severe								
	Life-threatening								
	Not Reported								
Diarrhea	None								
	Mild								
	Moderate								
	Severe								
	Life-threatening								
	Not Reported								
Fatigue	None								
	Mild								
	Moderate								

**Table 28: Number and Percentage of Participants Experiencing Solicited Events by Symptom, Severity, and Day Post Dosing – 3 mg/kg EV68-228-N (continued)**

Symptom	Severity	3 mg/kg EV68-228-N (N=X)							
		Day 1		Day 2		Day 3		Ongoing After Day 3	
		n	%	n	%	n	%	n	%
	Severe								
	Life-threatening								
	Not Reported								
Myalgia	None								
	Mild								
	Moderate								
	Severe								
	Life-threatening								
	Not Reported								

Notes: N=Number of participants in the Safety Population. Severity is the maximum severity reported post dosing for each participant for each day.

Tables with similar format:

**Table 29: Number and Percentage of Participants Experiencing Solicited Events by Symptom, Severity, and Day Post Dosing – 10 mg/kg EV68-228-N**

**Table 30: Number and Percentage of Participants Experiencing Solicited Events by Symptom, Severity, and Day Post Dosing – 30 mg/kg EV68-228-N**

**Table 31: Number and Percentage of Participants Experiencing Solicited Events by Symptom, Severity, and Day Post Dosing – Placebo**

**14.3.1.2 Unsolicited Adverse Events****Table 32: Summary of Unsolicited Adverse Events by MedDRA System Organ Class, High Level Group Term and Preferred Term and Dose Cohort**

MedDRA System Organ Class	MedDRA High Level Group Term	MedDRA Preferred Term	3 mg/kg EV68-228-N (N=X)				10 mg/kg EV68-228-N (N=X)				30 mg/kg EV68-228-N (N=X)				Placebo (N=X)				All Participants who Received Active Product (N=X)					
			n	%	95% CI a	Events	n	%	95% CI a	Events	n	%	95% CI a	Events	n	%	95% CI a	Events	n	%	95% CI a	Events		
Any SOC	Any HLGT	Any PT	x	xx	xx, xx	x	x	xx	xx, xx	x	x	xx, xx	x	x	xx	xx, xx	x	x	xx, xx	x	x	xx, xx	x	
[SOC 1]	Any HLGT	Any PT																						
	HLGT1	Any PT																						
		[PT 1]																						
		[PT 2]																						
		HLGT2																						
	Any HLGT	Any PT																						
	HLGT1	Any PT																						
		[PT 1]																						
		[PT 2]																						
		HLGT2																						
	Any HLGT	Any PT																						
	HLGT1	Any PT																						
		[PT 1]																						
		[PT 2]																						
		HLGT2																						

Notes: N=Number of participants in the Safety Population. This table presents the number and percentage of participants. A participant is only counted once per PT.

a The 95% CI of the proportion will be calculated using Clopper-Pearson (Exact) methodology from a binomial distribution.

**Table 33: Unsolicited Adverse Events by MedDRA System Organ Class, High Level Group Term and Preferred Term, Maximum Severity, and Dose Cohort**

MedDRA System Organ Class	MedDRA High Level Group Term	MedDRA Preferred Term	Severity	3mg/kg EV68-228-N (N=X)		10 mg/kg EV68-228-N (N=X)		30 mg/kg EV68-228-N (N=X)		Placebo (N=X)		All Participants who Received Active Product (N = X)	
				n	%	n	%	n	%	n	%	n	%
Any SOC	Any HLTG	Any PT	Any Severity	x	xx	x	xx	x	xx	x	xx	x	xx
			Mild	x	xx	x	xx	x	xx	x	xx	x	xx
			Moderate	x	xx	x	xx	x	xx	x	xx	x	xx
			Severe	x	xx	x	xx	x	xx	x	xx	x	xx
			Life-threatening	x	xx	x	xx	x	xx	x	xx	x	xx
SOC 1	Any HLTG	Any PT	Any Severity	x	xx	x	xx	x	xx	x	xx	x	xx
			Mild	x	xx	x	xx	x	xx	x	xx	x	xx
			Moderate	x	xx	x	xx	x	xx	x	xx	x	xx
			Severe	x	xx	x	xx	x	xx	x	xx	x	xx
			Life-threatening	x	xx	x	xx	x	xx	x	xx	x	xx
	HLGT1	PT1	Any Severity	x	xx	x	xx	x	xx	x	xx	x	xx
			Mild	x	xx	x	xx	x	xx	x	xx	x	xx
			Moderate	x	xx	x	xx	x	xx	x	xx	x	xx
			Severe	x	xx	x	xx	x	xx	x	xx	x	xx
			Life-threatening	x	xx	x	xx	x	xx	x	xx	x	xx
		PT2	Any Severity	x	xx	x	xx	x	xx	x	xx	x	xx
			Mild	x	xx	x	xx	x	xx	x	xx	x	xx
			Moderate	x	xx	x	xx	x	xx	x	xx	x	xx
			Severe	x	xx	x	xx	x	xx	x	xx	x	xx
			Life-threatening	x	xx	x	xx	x	xx	x	xx	x	xx

Notes: N=Number of participants in the Safety Population. This table presents the number and percentage of participants. A participant is only counted once by the maximal severity per PT.

**Table 34: Unsolicited Adverse Events by MedDRA System Organ Class, High Level Group Term and Preferred Term, Maximum Severity, Relationship, and Dose Cohort**

MedDRA System Organ Class	MedDRA High Level Group Term	MedDRA Preferred Term	Severity	3 mg/kg EV68-228-N (N=X)		10 mg/kg EV68-228-N (N=X)		30 mg/kg EV68-228-N (N=X)		Placebo (N=X)		All Participants who Received Active Product (N = X)					
				Related		Not Related		Related		Not Related		Related		Not Related		Related	
				n	%	n	%	n	%	n	%	n	%	n	%	n	%
Any SOC	Any HLG	Any PT	Any Severity	x	xx	x	xx	x	xx	x	xx	x	xx	x	xx	x	xx
			Mild	x	xx	x	xx	x	xx	x	xx	x	xx	x	xx	x	xx
			Moderate	x	xx	x	xx	x	xx	x	xx	x	xx	x	xx	x	xx
			Severe	x	xx	x	xx	x	xx	x	xx	x	xx	x	xx	x	xx
			Life-threatening	x	xx	x	xx	x	xx	x	xx	x	xx	x	xx	x	xx
SOC 1	Any HLG	Any PT	Any Severity	x	xx	x	xx	x	xx	x	xx	x	xx	x	xx	x	xx
			Mild	x	xx	x	xx	x	xx	x	xx	x	xx	x	xx	x	xx
			Moderate	x	xx	x	xx	x	xx	x	xx	x	xx	x	xx	x	xx
			Severe	x	xx	x	xx	x	xx	x	xx	x	xx	x	xx	x	xx
			Life-threatening	x	xx	x	xx	x	xx	x	xx	x	xx	x	xx	x	xx
	HLGT1	Any PT	Any Severity	x	xx	x	xx	x	xx	x	xx	x	xx	x	xx	x	xx
			Mild	x	xx	x	xx	x	xx	x	xx	x	xx	x	xx	x	xx
			Moderate	x	xx	x	xx	x	xx	x	xx	x	xx	x	xx	x	xx
			Severe	x	xx	x	xx	x	xx	x	xx	x	xx	x	xx	x	xx
			Life-threatening	x	xx	x	xx	x	xx	x	xx	x	xx	x	xx	x	xx
	PT 1	PT 1	Any Severity	x	xx	x	xx	x	xx	x	xx	x	xx	x	xx	x	xx
			Mild	x	xx	x	xx	x	xx	x	xx	x	xx	x	xx	x	xx
			Moderate	x	xx	x	xx	x	xx	x	xx	x	xx	x	xx	x	xx
			Severe	x	xx	x	xx	x	xx	x	xx	x	xx	x	xx	x	xx
			Life-threatening	x	xx	x	xx	x	xx	x	xx	x	xx	x	xx	x	xx

**Table 34: Unsolicited Adverse Events by MedDRA System Organ Class, High Level Group Term and Preferred Term, Maximum Severity, Relationship, and Dose Cohort (continued)**

PT 2	PT 2	PT 2	Any Severity	x	xx																		
			Mild	x	xx																		
			Moderate	x	xx																		
			Severe	x	xx																		
			Life-threatening	x	xx																		

Notes: N=Number of participants in the Safety Population. This table presents the number and percentage of participants. A participant is only counted once by the maximum severity per PT.

**Table 35: Related Unsolicited Adverse Events Post Dosing by MedDRA System Organ Class, High Level Group Term and Preferred Term, and Dose Cohort**

MedDRA System Organ Class	MedDRA High Level Group Term	MedDRA Preferred Term	3 mg/kg EV68-228-N (N=X)			10 mg/kg EV68-228-N (N=X)			30 mg/kg EV68-228-N (N=X)			Placebo (N=X)			All Participants who Received Active Product (N=X)		
			n	%	Events	n	%	Events	n	%	Events	n	%	Events	n	%	Events
Any SOC	Any HLTG	Any PT	x	xx	x	x	xx	x	x	xx	x	x	xx	x	x	xx	x
[SOC 1]	Any HLTG	Any PT															
	HLGT1	Any PT															
		[PT 1]															
		[PT 2]															
	HLGT2	Any PT															
		[PT 1]															
		[PT 2]															

Notes: N=Number of participants in the Safety Population. This table presents the number and percentage of participants. A participant is only counted once per PT.

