### **3.2. Outcome Measures**

##### **3.2.1. Primary**

- Proportion of participants experiencing solicited adverse events (AEs) through 48 hours post-infusion.
- Proportion of participants experiencing unsolicited AEs – including clinical and laboratory AEs – through Day 29.
- Proportion of participants experiencing serious AEs (SAEs), medically attended AEs (MAAEs), and new onset chronic medical conditions (NOCMCs) through the end of the study.

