## 4. INVESTIGATIONAL PLAN

### 4.1. Overall Study Design and Plan

This is a Phase 1, randomized, placebo-controlled, double-blinded study to assess the safety and PK of single IV administrations of EV68-228-N in healthy adult volunteers.

Three doses (3, 10 and 30 mg/kg) of EV68-228-N will be evaluated in three separate, sequential cohorts (N = 12, each cohort) in this single dose escalation study. The cohorts will be randomized in a 5:1 randomization scheme for EV68-228-N and placebo. The first two participants in each cohort will serve as sentinels. Sentinel participants may be located at different sites. Sentinel safety data will be collected through Day 3 before submitting to the Protocol Review Safety Team (PSRT) for review. The PSRT is comprised of the Principal Investigator (PI), the DMID Medical Monitor, and the DMID Medical Officer.

Data to be reviewed will include clinical data collected from Visits 1, 2 and 3, the results of laboratory testing conducted at these visits, solicited AEs and the passive reporting of AEs through Day 3. From the time of infusion of the sentinels to at least 48 hours after infusion, no new participants will be given study product or placebo, but screening may continue. If no safety signal is detected in the sentinel group, and after approval from the DMID Medical Monitor, the remaining 10 participants in the cohort will be dosed following the overall 5:1 randomization scheme.

All participants will be actively monitored for AEs and safety laboratory data following dosing through Day 8. Data will be reviewed by the PSRT and discussed with the SMC for their concurrence before advancing to the next cohort. Electronic review of the safety data by the SMC is required prior to the cohort dose escalation when halting rules are met or there are any safety concerns.

Assuming no safety concerns are identified after review of the first cohort safety data through Day 8, enrollment of Cohort 2 will begin. The dose of EV68-228-N will be increased to 10 mg/kg for the second cohort. The same sentinel design and safety plan will be used to evaluate sentinel participants in Cohort 2 and determine whether to enroll the remaining participants in Cohort 2. In addition, the same sentinel design and safety plan will be used for Cohort 3, which will evaluate the 30 mg/kg dose.

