## 4.2. Discussion of Study Design

This is a Phase 1, randomized, placebo-controlled, double-blinded study to assess the safety and PK of a single IV infusion of EV68-228-N in healthy adult volunteers. All participants will be actively monitored for solicited AE following infusion through Day 3 and clinical and safety laboratory data following dosing through Day 8. Three doses (3, 10 and 30 mg/kg) of EV68-228-N will be evaluated in three separate, sequential cohorts in this single dose escalation study. The cohorts will be randomized in a 5:1 randomization scheme. All placebo participants are analyzed jointly across cohorts. The first two participants in each cohort will serve as sentinels. Sentinel participants may be located at different sites.

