## 5. SAMPLE SIZE CONSIDERATIONS

As a Phase 1, first-in-human study, the number of participants was chosen principally on feasibility and using a 5:1 randomization scheme. Thus, three cohorts of 10 participants each (n=30) and 6 placebo recipients (total N=36) are proposed. With 10 participants in each cohort receiving study product, the chance of observing at least one AE of probability 20% or more is approximately 89.3% (see [Table 3](#)). Therefore, if no AEs of a given type occur in an active dose group, we can be relatively confident that they will occur in fewer than 20% of people once the treatment is implemented.

PK parameters are not a primary outcome of the study, so it has not been powered for this, however with a sample size of 10 participants per dose level, assuming the pharmacokinetics are not dose proportional, a parameter with a coefficient of variation of 120% or less has a 90% chance to be observed within 80% and 120% of the geometric mean.

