### 9.3.1. **Solicited Events and Symptoms**

Solicited AEs will be collected from the end of the infusion through Day 3. Solicited AEs will be summarized by severity for each day post administration (Days 1-3) and as the maximum severity over all 3 days.

Additionally, solicited AEs will be analyzed using standard techniques, such as exact CIs, to summarize the proportion of participants reporting each symptom. Solicited AEs include headache, rash, nausea, vomiting, diarrhea, fatigue, and myalgia.

The proportion of participants reporting at least one solicited AE will be summarized for each solicited AE. The 95% CI calculated using Clopper-Pearson methodology from a binomial distribution (SAS Proc Freq with a binomial option) will be presented (Table 25).

- The maximum severity of solicited symptoms per participant by day will be presented graphically in Figure 3.
- The proportion of participants experiencing solicited events, Clopper-Pearson 95% CI, and difference of proportion from the placebo group will be summarized in Table 26.
- The number and percentage of participants experiencing solicited events by symptom, maximum severity, will be summarized in Table 27.
- The number and percentage of participants experiencing solicited events by symptom, maximum severity and day after infusion will be summarized in Table 28, Table 29, Table 30, and Table 31.
- Solicited AEs by participant will be presented in Listing 11.

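### Table 26 puts Wald intervals on the solicited-AE differences from placebo (10 vs 6 participants); these shrink to zero width when no events occur and cover well below 95% at most plausible rates

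*SAP*

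**What the plan says.** Section 3.2.1 lists as the first primary outcome "Proportion of participants experiencing solicited adverse events (AEs) through 48 hours post-infusion". Section 9.3.1 sends the comparison with placebo to Table 26: "Clopper-Pearson 95% CI, and difference of proportion from the placebo group will be summarized in Table 26". That sentence names an interval method for the single proportions and none for the difference. The method for the difference appears only in the Table 26 shell. Footnote a, for the proportions, reads "95% CI=Clopper-Pearson confidence interval"; footnote b, for the differences, reads "95% CI=Wald confidence interval". The shell has a row block for any symptom and one for each of seven symptoms, with a difference and interval for each of the three doses.

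Section 5 sets the group sizes: "three cohorts of 10 participants each (n=30) and 6 placebo recipients (total N=36) are proposed". Section 4.2 makes the comparator the pooled placebo group: "All placebo participants are analyzed jointly across cohorts". No passage gives a continuity correction, a rule for zero cells, or an expected solicited-AE rate.

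**The concern.** The Wald interval takes its standard error from the observed proportions. When an observed proportion is 0 or 1, that group contributes no variance; when both are, the interval has no width. With 6 placebo participants an observed zero is likely for any uncommon symptom, so the weakness affects ordinary results in this table.

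Two misleading outputs follow. A symptom seen in neither group would be reported as a difference of zero with a 95% interval of (0.00, 0.00), as if absence of excess risk were established. A symptom seen in a few active participants and no placebo participants could be shown with an interval excluding zero when the data do not support that. The first error reassures falsely and the second alarms falsely. Both would appear in the safety tables of a first-in-human study.

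**Working it through.** **Inputs.** Active n = 10 and pooled placebo n = 6 (Sections 4.2 and 5); two-sided 95%, so z = 1.96; uncorrected Wald (Table 26, footnote b). True event rates are assumed, because the SAP gives none. I take mainly 5% to 30%, the range of SAP Table 3, and extend it where stated.

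**The plan's own figure.** Section 5 gives 89.3% for seeing at least one AE of true rate 20% among 10 participants: 1 - 0.8^10 = 0.893. It reproduces, as do all six rows of Table 3.

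**Formula.** With observed proportions a (active) and b (placebo), Wald is (a - b) ± 1.96 × sqrt[a(1-a)/10 + b(1-b)/6].

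**0/10 against 0/6.** The standard error is sqrt(0 + 0) = 0, so the interval is (0.00, 0.00). Clopper-Pearson upper limits in the same table would be 0.31 for 0/10 and 0.46 for 0/6. Other methods for the difference give:

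| Method | 95% interval |
|---|---|
| Wald | (0.00, 0.00) |
| Newcombe | (-0.39, 0.28) |
| Miettinen-Nurminen | (-0.41, 0.29) |

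**How often.** The probability is (1 - p1)^10 × (1 - p0)^6 per symptom and dose:
- 5% in both groups: 0.95^16 = 44%
- 10% active, 5% placebo: 0.90^10 × 0.95^6 = 26%
- 10% in both groups: 0.90^16 = 18.5%

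Seven symptoms by three doses make 21 such intervals. If every symptom had the stated rates, the expected number of zero-width intervals would be 21 × 0.44 = 9.2, 21 × 0.256 = 5.4 and 21 × 0.185 = 3.9 respectively.

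**3/10 against 0/6.** The difference is 0.30 and the standard error is sqrt(0.3 × 0.7/10 + 0) = 0.145, so Wald is 0.30 ± 0.284 = (0.016, 0.584). Miettinen-Nurminen is (-0.158, 0.612) and Newcombe is (-0.135, 0.603). Fisher's exact two-sided p is C(10,3)/C(16,3) + C(6,3)/C(16,3) = 120/560 + 20/560 = 0.25.

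**Exact coverage.** All 11 × 7 outcomes were enumerated and weighted by their binomial probabilities:

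| True rates, active / placebo | Wald | Newcombe | Miettinen-Nurminen |
|---|---|---|---|
| 5% / 5% | 99.0% | 99.9% | 99.9% |
| 10% / 10% | 95.6% | 99.3% | 99.3% |
| 10% / 5% | 72.2% | 98.8% | 98.8% |
| 5% / 20% | 72.7% | 98.6% | 98.9% |
| 20% / 5% | 86.8% | 97.0% | 99.5% |
| 20% / 20% | 89.2% | 97.5% | 97.5% |
| 30% / 30% | 87.5% | 95.8% | 95.8% |
| 50% / 50% | 87.4% | 94.3% | 94.3% |

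At 10% / 5% most of the shortfall is the zero-width case: it occurs 25.6% of the time and always misses the true difference of 0.05. Over a grid of rates from 1% to 30% in each group, mean Wald coverage is 80.9%, and 98.9% of grid points fall below 95%. Mean coverage on that grid is 97.8% for Newcombe and 97.6% for Miettinen-Nurminen.

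**Exclusion of zero when the rates are equal** is 100% minus the equal-rate coverage. Wald excludes zero in 10.8%, 12.5% and 12.6% of cases at 20%, 30% and 50%; Miettinen-Nurminen does so in 2.5%, 4.2% and 5.7%.

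**Continuity correction.** The SAP states none. Adding one gives (-0.13, 0.13) at 0/10 against 0/6, still far narrower than the score-type intervals. Its coverage falls to about 60% at its worst point on a 1% to 99% grid.

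**The case against.** The primary outcome is the proportion within each group, and its intervals are Clopper-Pearson. The difference is an additional descriptive row: Section 6.8 says the primary analyses are not hypothesis tests. Dose escalation rests on safety review by the PSRT and SMC (Section 4.1), and these intervals are produced only at the final analysis. No rule treats an interval excluding zero as a signal. A reader who sees (0.00, 0.00) also sees the wide single-group limits in the rows above.

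The event rates are assumptions, and the two failures arise mainly at different rates. At 5% in both groups, where zero width is most frequent of the cases shown, Wald covers 99.0%; at 10% in both groups it covers 95.6%. The 11-13% false exclusion needs equal rates of 20-50%, where zero width has probability 2.8% or less. That figure is also two-sided: exclusion toward harm from the active product is 8.7% at 20% and 6.3% at 50%.

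All of this is accurate, and it limits the harm to misleading precision in the study report. It does not rescue the method. Coverage at equal low rates is adequate partly because a zero-width interval at zero trivially contains a true difference of zero; once the rates differ slightly, coverage falls to 72%. Single-group limits of 0.31 and 0.46 beside a difference known exactly make the table contradict itself. Where no test is planned, the interval is the only statement of uncertainty about the comparison.

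**Conclusion.** The concern holds. Footnote b is the only specification of the interval for the difference, and at 10 against 6 participants an uncorrected Wald interval is unsuitable. The zero-width result at 0/10 against 0/6 and the exclusion of zero at 3/10 against 0/6 follow from the planned group sizes alone. How often they occur, and the coverage figures, depend on the assumed rates: zero width in 18.5-44% of symptom-by-dose intervals for rates of 5-10%, and coverage of 72-93% for the unequal pairs examined (93% at 30% active and 10% placebo). Undercoverage is widespread but not universal, since Wald reaches nominal coverage at equal rates of 5% and 10%. Point estimates, single-group intervals and dose escalation are unaffected. The footnote needs correcting before the tables are produced, because this is the SAP's only active-versus-placebo interval and it concerns a primary safety outcome.

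**What to change.** In Table 26, replace the method in footnote b with a Miettinen-Nurminen score interval, and state the same method in Section 9.3.1, which at present names none for the difference. Newcombe or an exact unconditional interval would also serve. Over the 1-99% grid, mean coverage is 96.2% for Miettinen-Nurminen and 95.3% for Newcombe, with minima of 91.4% and 88.2%. Make the change before unblinding, so that the method is not chosen with the results in view.

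The cost is a different interval option in the table program and two short edits to the SAP. Sample size, data collection and conduct do not change. The intervals will usually be wider: at 3/10 against 0/6 the width goes from 0.57 to 0.77, and at 0/10 against 0/6 from 0 to 0.70.

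### Table 27's footnote takes maximum severity over all solicited symptoms, a rule that fits only the Any Symptom rows and contradicts the per-symptom rows and Section 9.3.1

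*SAP*

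**What the plan says.** The title of SAP Table 27 is "Number and Percentage of Participants Experiencing Solicited Events by Symptom, Maximum Severity, and Dose Cohort". The shell has rows from None to Life-threatening for Any Symptom and for headache, rash, nausea, vomiting, diarrhea, fatigue and myalgia. The footnote states: "Severity is the maximum severity reported over all solicited symptoms post dosing for each participant". It covers the whole table, and no implementation note gives a separate rule for the single-symptom rows.

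Section 9.3.1 describes the same table differently: "The number and percentage of participants experiencing solicited events by symptom, maximum severity, will be summarized in Table 27". It also says what the maximum is taken over: "Solicited AEs will be summarized by severity for each day post administration (Days 1-3) and as the maximum severity over all 3 days". Section 4.5.1 likewise takes the maximum over the three days.

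**The concern.** A maximum over all solicited symptoms is a single grade for each participant. It suits the Any Symptom block, where the row pools the symptoms. In a headache or rash block it replaces the grade of that symptom with the grade of whatever symptom was worst.

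Among the planned tables and figures, Table 27 is the only one that sets maximum severity per symptom over Days 1-3 side by side across the three doses and placebo. Tables 25 and 26 carry no severity, Tables 28 to 31 are by day and one arm each, and Figure 3 is by day. If the footnote were followed, this display could show moderate or severe grades for symptoms that were only mild. If it were not followed, the printed footnote would misdescribe the numbers above it.

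**Working it through.** The plan states no figure on this point, so there is none to reproduce. The check has two parts: a comparison of the severity rules, and an illustration with assumed data.

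**Severity rules side by side**

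| Place in the SAP | Maximum taken over | Pools over symptoms or terms? |
|---|---|---|
| Table 27 footnote | All solicited symptoms after dosing | Yes |
| Table 27 title and rows | Laid out by symptom | No, except Any Symptom |
| Sections 4.5.1 and 9.3.1 | The three days | No |
| Table 28 footnote: "Severity is the maximum severity reported post dosing for each participant for each day" | Each day | Not stated, so the row label governs |
| Table 33 footnote (unsolicited events): "A participant is only counted once by the maximal severity per PT" | Events within the row's own term | No |

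Only the Table 27 footnote pools over symptoms.

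**Illustration (assumed data, one active arm of 10)**

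- Participant 1: mild headache, severe nausea.
- Participant 2: mild headache, moderate fatigue.
- Participant 3: mild headache only.
- Participant 4: mild myalgia only.
- Participants 5 to 10: no symptoms.

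Three rules were applied to each symptom block:

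- A: the participant's maximum for that symptom over Days 1-3.
- B: the footnote, applied only to participants who report that symptom.
- C: the footnote, applied to every participant (fully literal).

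Counts are None/Mild/Moderate/Severe/Life-threatening:

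| Block | A | B | C |
|---|---|---|---|
| Any Symptom | 6/2/1/1/0 | 6/2/1/1/0 | 6/2/1/1/0 |
| Headache | 7/3/0/0/0 | 7/1/1/1/0 | 6/2/1/1/0 |
| Rash | 10/0/0/0/0 | 10/0/0/0/0 | 6/2/1/1/0 |
| Nausea | 9/0/0/1/0 | 9/0/0/1/0 | 6/2/1/1/0 |
| Fatigue | 9/0/1/0/0 | 9/0/1/0/0 | 6/2/1/1/0 |
| Myalgia | 9/1/0/0/0 | 9/1/0/0/0 | 6/2/1/1/0 |

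Vomiting and diarrhea behave as rash does.

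- The Any Symptom block is the same under all three rules, so the footnote is correct there.
- Under B, two of the three mild headaches appear as moderate and severe. Participant 3's headache stays mild because it is that participant's worst symptom. The number affected, 10 - 7 = 3, still agrees with what Table 25 would show.
- Under C, every symptom block equals Any Symptom. Rash shows 10 - 6 = 4 of 10 affected though nobody reported it, whereas Table 25 would show 0.

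**Size per misgraded participant**

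Arm sizes come from Section 5 and Table 1.

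- Active arm: 1/10 = 10 percentage points in the cell concerned.
- Pooled placebo: 1/6 = 16.7, about 17 percentage points.

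**The case against.** The strongest reply is that nobody would build the table this way. The title, the row layout and Sections 4.5.1 and 9.3.1 all point to a maximum per symptom over the three days. The fully literal reading makes seven of the eight blocks copies of the first. A misgraded Table 27 would also clash with Tables 28 to 31, which show severity by symptom and day, and with Listing 11, which shows it per participant, symptom and day. All of this stands, and it limits the point to a wrong rule in a table shell whose intended version can be recovered. It does not make the footnote right: it is the only severity rule printed with the table and would appear in the report. Reading B is also less conspicuous than C, because it leaves the symptom counts in agreement with Table 25.

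A reader might infer three stronger things, none of which the SAP supports.

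- *That a primary outcome is distorted.* The first primary outcome in Section 3.2.1 is the proportion of participants with solicited events, which is occurrence. Tables 25 and 26 report it by symptom with exact intervals, and the footnote does not reach them.
- *That every mild symptom would be inflated.* Among reported symptoms, only those milder than the participant's worst would be.
- *That the SAP leaves the rule for single symptoms unsettled.* Section 9.3.1 settles it; the footnote contradicts it.

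**Conclusion.** The point holds as a wrong rule in a supporting severity display. The Table 27 footnote is correct for Any Symptom and incorrect for the seven symptom blocks, where it conflicts with the table's title and rows and with Section 9.3.1. The shift of 10 or about 17 percentage points per misgraded participant rests on the planned arm sizes. How many participants would be affected depends on how often someone has symptoms of different grades, which the SAP does not give; the cohort above is assumed for illustration only. The planned analysis as set out in the body text is sound, so the priority is low, but the footnote should not go into the report as it stands.

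**What to change.** Replace the severity sentence in the Table 27 footnote with: *For each symptom, severity is the participant's maximum severity of that symptom over Days 1-3; for Any Symptom, it is the maximum over all solicited symptoms over Days 1-3.*

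The cost is one footnote. No data collection, sample size, analysis population or planned method changes, and a table programmed from Section 9.3.1 needs no reprogramming. The version history shows that version 2.0 was issued to correct a table number and title on a continuation page, so a correction of this size is in keeping with how the SAP has been maintained.
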